## 9 TREATMENTS ADMINISTERED

## 9.1 Investigational Product(s)

[figure not shown]
*Test Product(s):* PRECISION1 soft contact lenses [REDACTED]

*Comparator Product(s) (If applicable):* Biotrue ONEday soft contact lenses [REDACTED]

**Table 9–1 Test Product**

Test Product	PRECISION1 soft contact lenses (PRECISION1)
Manufacturer	Alcon Laboratories, Inc. [name]

	[name] USA
Indication for use and intended purpose in the current study	Precision1 (verofilcon A) spherical soft contact lenses are indicated for the optical correction of refractive ametropia (myopia and hyperopia) in phakic or aphakic persons with nondiseased eyes with up to approximately 1.50 diopters (D) of astigmatism that does not interfere with visual acuity. The lenses are to be prescribed for single use, daily disposable wear. The lenses are not intended to be cleaned or disinfected and should be discarded after a single use.
Product description and parameters available for this study	

• Material: verofilcon A

• Water content: 51%

• Power range: -1.00 to -6.00 D, 0.25 D steps

• Base curve (mm): 8.3

• Diameter (mm): 14.2

Formulation	Please refer to package insert.
Usage	

• Wear:

○ Daily Wear

○ Bilateral

• Replacement period: Daily Disposable

• Exposure:

○ 16 days total duration (test and comparator)

■ Test Product: 8 (-0/+3) days

■ Comparator Product: 8 (-0/+3) days

• Lens Care: N/A

Number/Amount of product to be provided to the subject	Subjects will be dispensed study lenses at Visit 1 and Visit 2. No spare lenses will be provided to the subject.

Packaging description	Blister foil pack
Labeling description	

• Lens Foil label includes:

- lens identifier

- base curve

- diameter

- packing solution

- power

- lot number

- expiration date

- content statement

- investigational device statement

- sponsor information

- country of origin

	
	
	
	
	
	
	
Storage conditions	Stored at room temperature.
	
	
Supply	Alcon will provide a fitting set and study lenses. Refer to the MOP for a detailed description

**Table 9–2** **Comparator Product**

Comparator Product(s)	Biotrue ONEday soft contact lenses (Biotrue)
Manufacturer	Bausch & Lomb Incorporated [name]

	[name] USA
Indication for Use	The Bausch + Lomb Biotrue ONEday (nesofilcon A) Soft (Hydrophilic) Contact Lens is indicated for the daily wear correction of refractive ametropia (myopia, hyperopia and astigmatism) in aphakic and/or nonaphakic persons with nondiseased eyes, exhibiting astigmatism of 2.00 diopters or less, that does not interfere with visual acuity.
Product description and parameters available for this study	

• Material: nesofilcon A

• Water content: 78%

• Power range: -1.00 to -6.00 D in 0.25 D steps

• Base curve (mm): 8.6

• Diameter (mm): 14.2

Formulation	Please refer to package insert.
Usage	

• Wear:

○ Daily Wear

○ Bilateral

• Replacement period: Daily Disposable

• Exposure:

○ 16 days total duration (test and comparator)

■ Test Product: 8 (-0/+3) days

■ Comparator Product: 8 (-0/+3) days

• Lens Care: N/A

Number/Amount of Product to be Provided to the subject	Subjects will be dispensed study lenses at Visit 1 and Visit 2. No spare lenses will be provided to the subject.
Packaging description	Blister foil pack

Labeling description	

• Lens Foil label includes:

- lens identifier

- base curve

- diameter

- packing solution

- power

- lot number

- expiration date

- content statement

- investigational device statement

- sponsor information

- country of origin

• [REDACTED]

• [REDACTED]

• [REDACTED]

• [REDACTED]

• [REDACTED]

• [REDACTED]

Storage conditions	Stored at room temperature.
	[REDACTED]
Supply	Alcon will provide a fitting set and study lenses. Refer to the MOP for a detailed description.

More information on the test and comparator products can be found in the respective Package Inserts.

## 9.2 Other Medical Device or Medication Specified for Use During the Study

No other medical devices or medications are required to be used in conjunction with the treatments during the clinical study.

## 9.3 Treatment Assignment / Randomization

Subjects will be randomized in a 1:1 ratio to receive treatment (lens) in crossover sequence: Test product then Comparator product or Comparator product then Test product, respectively.

Sequence	EDC/randomization integration system	Lens Name
Sequence 1	[REDACTED]	PRECISION1/Biotrue
Sequence 2	[REDACTED]	Biotrue/PRECISION1

Only after signing the ICF, a subject will be assigned a subject number by the electronic data capture system.

A randomization list will be generated using a validated system that automates the random assignment of treatments (lens sequence) to randomization numbers in the specified ratio. Subjects will be assigned treatment (lens sequence) according to the randomization list uploaded in the randomization system. The randomization list will be generated and maintained by the study sponsor.

At Visit 1, all eligible subjects will be randomized via the EDC/randomization integration system to one of the treatment arms. The investigator or delegate will access the respective system after confirming that the subject meets all the eligibility criteria. A randomization number will be automatically assigned to the subject according to the subject randomization list but will not be communicated to the site user. The EDC/randomization integration system will inform the site user of the treatment (lens sequence) assignment to be dispensed to the subject.

## 9.4 Treatment masking

This study is double-masked, with subjects randomized to use PRECISION1 contact lenses or Biotrue contact lenses for the duration of a 1-week treatment period per lens type. ■

[REDACTED] Unmasking will occur only after all planned study data have been validated, and the database locked.

Masked study personnel must avoid seeking information that may compromise masking.

[REDACTED]

[REDACTED]

[REDACTED]

In the event of a medical emergency where the knowledge of subject treatment is required, an individual investigator will have the ability to unmask the treatment assignment for a specific subject after contacting an appropriate study sponsor representative if time allows.

## 9.5 Accountability Procedures

Upon receipt of the IPs, the investigator or delegate must conduct an inventory. During the study, the masked investigator must designate study staff to provide the IPs to the subjects in accordance with their randomization assignment. Throughout the study, the investigator or delegate must maintain records of IP dispensation and collection for each subject. This record must be made available to the study monitor for the purposes of verifying the accounting of IP supplies. Any discrepancies and/or deficiencies between the observed disposition and the written account must be recorded along with an explanation. All IPs sent to the investigator must be accounted for by study sponsor personnel, and in no case be used in an unauthorized situation.

The investigator should make every effort to collect unused lenses, foils, and supplies from subjects.

It is the investigator's responsibility to ensure that:

- All study products are accounted for and not used in any unauthorized manner
- All unused products are available for return to the study sponsor, as directed

- Any study lenses associated with a device deficiency or with any product-related adverse event (i.e., ADE or SADE) are returned to the study sponsor for investigation, unless otherwise directed by the sponsor. Refer to Section 11 of this protocol for additional information on the reporting of device deficiencies and AEs and the return of study products associated with these events.

The investigator is responsible for proper disposition of all unused IPs at the conclusion of the study, according to the instructions provided in the MOP.

## **9.6 Changes to concomitant medications, treatments/ procedures**

After the subject is enrolled into the study, the investigator must instruct the subject to notify the study site about:

- Any new medications
- Alterations in dose or dose schedules for current medications,
- Any medical procedure or hospitalization that occurred or is planned
- Any nondrug therapies (including physical therapy and blood transfusions).

The investigator must document this information in the subject's case history source documents.

## **10 STUDY PROCEDURES AND ASSESSMENTS**

Subjects will be expected to attend 3 office visits, as shown below.

Visit #	Visit Type	Visit Window
Visit 1	Screening/Baseline/Dispense Lens 1	N/A
Visit 2	Week 1 Follow-up Lens 1/Dispense Lens 2	8 (-0/+3) days after Visit 1
Visit 3	Week 1 Follow-up Lens 2/Exit	8 (-0/+3) days after Visit 2

Unscheduled Visits and Early Exit Visits are allowed, if necessary.

Study lenses will be provided to the subjects to take home for daily wear during the course of the trial.

Study randomization will occur at Visit 1 with assigned lenses provided to take home at Visit 1 and Visit 2. Study contact lens fitting will occur at Visit 1 for both study lenses. If a subject cannot be successfully fit (either study lens) according to the study lens fitting guides as determined by the investigator, they will be required to exit from the study.

Lubrication/rewetting drops will not be permitted during this study.

Study tests, procedures, and questionnaires will be conducted as outlined in the MOP.

## **10.1 Informed Consent and Screening**

The investigator or delegate must explain the purpose and nature of the study, and have the subject read, sign, and date the IRB/IEC-approved informed consent document. The subject must sign the ICF BEFORE any study-specific procedures or assessments can be performed, including study-specific screening procedures. Additionally, have the individual obtaining consent from the subject and a witness, if applicable, sign and date the informed consent document.

The investigator or delegate must provide a copy of the signed document to the subject and place the original signed document in the subject's chart, or provide documentation as required by local regulations.

## **10.2 Description of Study Procedures and Assessments**

Detailed descriptions of assessments and procedures are provided in the MOP. The investigator is responsible for ensuring responsibilities for all procedures and assessments are delegated to appropriately qualified site personnel.

### **10.2.1 Demographics**

Obtain demographic information including age, race, ethnicity, and sex.

### **10.2.2 Medical History**

Collect medical history information, including information on all medications used within the past 30 days. Include herbal therapies, vitamins, and all over-the-counter as well as prescription medications. Throughout the subject's participation, obtain information on any changes in medical health and/or the use of concomitant medications.

Medical History and Concomitant Medications will be collected in the eCRF as outlined in the MOP.

### **10.2.3 Investigational Product compliance**

Review subject compliance with the IP usage and adjunct product usage and collect all used and unused study IPs and other products that were dispensed.

### **10.2.4 Adverse Event Collection: Safety Assessment**

Assess and record any adverse events that are observed or reported since the previous visit, including those associated with changes in concomitant medication dosing in the subject source documents. See Section 11 for further details regarding AE collection and reporting. Note: AEs must be recorded for all enrolled subjects from the time of signature of informed consent, regardless of subject enrollment status (screen failure or randomized).

### **10.2.5 Slit Lamp Biomicroscopy: Safety Assessment**

SLE of the cornea, iris/anterior chamber and lens must be performed in both eyes before instillation of any diagnostic eye drops.

### **10.2.6 Device Deficiencies: Safety Assessment**

Assess and record any Device Deficiencies that are reported or observed since the previous visit. Requirements for reporting device deficiencies in the study can be found in Section 11. Device deficiencies on comparator lenses should be reported per the manufacturer's guidelines. Note: Device deficiencies must be recorded for all enrolled subjects from the time of signature of informed consent, regardless of subject enrollment status (screen failure or randomized).

[REDACTED]

[REDACTED]

[REDACTED]

## **10.3 Unscheduled Visits**

If a subject visit occurs between any regularly scheduled visit and the visit is conducted by study personnel, this visit must be documented as an Unscheduled Visit. If the subject seeks medical attention outside the clinic (for example, at an Emergency Room) or at the clinic but is seen by nonstudy personnel, the investigator is to capture adverse event-related information on the Adverse Event form upon becoming aware.

During all unscheduled visits, the investigator must conduct the following procedures:

- Collect Adverse Event information
- Record changes in medical condition or concomitant medication
- Collect device deficiency information
- Biomicroscopy

The investigator may perform additional procedures for proper diagnosis and treatment of the subject according to Table 3-1 or at their discretion. The investigator must document this information in the subject's case history source documents.

If during an Unscheduled Visit the subject is discontinuing the IP or discontinuing from the study, the investigator must conduct Exit procedures according to Table 3-1 Schedule of Study Procedures and Assessments, as possible.

## **10.4 Discontinued Subjects**

### **10.4.1 Screen Failures**

Subjects who were excluded from the study after signing the informed consent and prior to randomization to study product assignment and dispensing of study product.

The investigator must document the reason for screen failure in the subject's case history source documents.

Subject numbers must not be re-used.

### **10.4.2 Discontinuations**

Discontinued subjects are individuals who voluntarily withdraw or are withdrawn from the study by the investigator after signing the informed consent.

Subject numbers of discontinued subjects must not be re-used (i.e., subject replacement is not allowed).

Subjects may discontinue from study or study treatment at any time for any reason. Subjects may also be discontinued from study treatment at any time if, in the opinion of the investigator, continued treatment poses a risk to their health.

If a subject discontinues from study treatment, every effort must be made to keep the subject in the study and to continue with the study assessments as specified in the schedule of study procedures and assessments until the final visit.

For subjects discontinuing from the study, the investigator must complete all Exit procedures according to Table 3-1 Schedule of Study Procedures and Assessments and Section 10.4.3, if the subject is willing and able, and if in the opinion of the investigator it is safe for the subject to do so.

The investigator must document the reason for study or treatment discontinuation in the subject's case history source documents.

To ensure the safety of all subjects who discontinue early, investigators must assess each subject and, if necessary, advise them of any therapies and/or medical procedures that may be needed to maintain their health.

#### **10.4.3 Schedule of Procedures and Assessments for Subjects Discontinued from Investigational Product**

Other than screen failures, if a subject discontinues from the study, the subject should undergo an Early Exit Visit. Refer to Table 3-1 and the MOP for details.

### **10.5 Clinical Study Termination**

The study sponsor reserves the right to suspend or close the investigational site or suspend or terminate the study in its entirety at any time.

If the clinical study is prematurely terminated or suspended by the study sponsor:

- The study sponsor must:
  - Immediately notify the investigator(s) and subsequently provide instructions for study termination.
  - Inform the investigator and the regulatory authorities of the termination/suspension and the reason(s) for the termination/suspension.
- The investigator must:
  - Promptly notify the IRB/IEC of the termination or suspension and of the reasons.

- Provide subjects with recommendations for poststudy treatment options as needed.

The investigator may terminate the site's participation in the study for reasonable cause.

Breaking of the masked treatment codes will be done after locking the database.

[figure not shown]
### 10.5.1 Follow-up of subjects after study participation has ended

Following this study, the subject will return to their eye care professional for their routine eye care.

## 11 ADVERSE EVENTS AND DEVICE DEFICIENCIES

[figure not shown]
An AE is any untoward medical occurrence, unintended disease or injury, or untoward clinical signs (including abnormal laboratory findings) in subjects, users, or other persons, whether or not related to the investigational medical device (*Test product*). Refer to the Glossary of Terms and figures below for categories of AEs and SAEs.

**Figure 11-1** Categorization of All AEs

**Figure 11-2**

**Categorization of All Serious Adverse Events**

### ***Device Deficiencies***

A device deficiency is inadequacy of a medical device with respect to its identity, quality, durability, reliability, safety, or performance. A device deficiency may or may not be associated with patient harm (i.e., ADE or SADE); however, not all ADEs or SADEs are due to a device deficiency. The investigator should determine the applicable category listed in the Device Deficiency eCRF for the identified or suspect device deficiency and report any patient harm separately. Examples of device deficiencies include the following:

- Len missing/folded/fragments/Lens cloudy/dirty
- Lens surface/edge defect
- Torn lens during handling/in pack
- Packaging deficit (e.g., blister strip damage, primary/secondary label mismatch, mislabeled product, tampered seal)
- Potential contaminant

## 11.1 Monitoring for Adverse Events

At each visit, after the subject has had the opportunity to spontaneously mention any problems, the investigator should inquire about AEs by asking the standard questions shown below and report as applicable:

- “Have you had any health problems since your last study visit?”
- “Have there been any changes in the medicines you take since your last study visit?”

Additionally, changes in *any protocol-specific parameters* [REDACTED] evaluated during the study are to be reviewed by the investigator. Any untoward (unfavorable and unintended) change in *a protocol-specific parameter* [REDACTED] that is clinically relevant, in the opinion of the investigator, is to be reported as an AE. These clinically relevant changes will be reported regardless of causality.

## 11.2 Procedures for Recording and Reporting

AEs are collected from the time of informed consent. Any preexisting medical conditions or signs/symptoms present in a subject prior to the start of the study (i.e., before informed consent is signed) are not considered AEs in the study and should be recorded in the Medical History section of the eCRF.

In addition, temporary lens awareness or visual changes during the fitting process are not considered AEs if the investigator assesses that the symptom(s) can reasonably resolve within the anticipated adaptation period.

For each recorded event, the ADEs and SAEs documentation must include: date of occurrence, severity, treatment (if applicable), outcome, and assessments of the seriousness and causality. In addition, the investigator must document all device deficiencies reported or observed with Test and Comparator products on the Device Deficiency eCRF. The site must submit all available information on ADEs, SAEs, and device deficiencies to the study sponsor immediately as follows

- All SAEs must be reported immediately (within 24 hours) of the investigator’s or site’s awareness.
- ADEs that do not meet seriousness criteria and Device deficiencies must be reported within 10 calendar days of the investigator’s or site’s awareness.
- A printed copy of the completed *Serious Adverse Event and Adverse Device Effect* and/or *Device Deficiency* eCRF must be included with product returns.

- Additional relevant information after initial reporting must be entered into the eCRF as soon as the data become available.
- Document all relevant information from Discharge Summary, Autopsy Report, Certificate of Death, etc., if applicable, in narrative section of the *Serious Adverse Event and Adverse Device Effect* eCRF.

*Note:* Should the EDC system become nonoperational, the site must complete the appropriate paper *Serious Adverse Event and Adverse Device Effect* and/or *Device Deficiency* Form. The completed form is emailed to the study sponsor at [[contact]](mailto:[contact]) according to the timelines outlined above; however, the reported information must be entered into the EDC system once it becomes operational.

Any AEs and device deficiencies for nonstudy marketed devices/products will be considered and processed as spontaneous (following the postmarket vigilance procedures) and should be communicated to the device's/product's manufacturer as per local requirements.

Study sponsor representatives may be contacted for any protocol-related question.

Further, depending upon the nature of the AE or device deficiency being reported, the study sponsor may request copies of applicable portions of the subject's medical records. The investigator must also report all AEs and device deficiencies that could have led to a SADE according to the requirements of regulatory authorities or IRB/IEC.

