Serious Adverse Event (SAE)	
Adverse event that led to any of the following:
 

• Death.

• A serious deterioration in the health of the subject, users or other persons as defined by one or more of the following:

a) a life-threatening illness or injury Note: Life-threatening means that the individual was at immediate risk of death from the event as it occurred, i.e., it does not include an event which hypothetically might have caused death had it occurred in a more severe form.

b) any potentially sight-threatening event or permanent impairment to a body structure or a body function including chronic diseases.

c) inpatient hospitalization or prolonged hospitalization.

d) a medical or surgical intervention to prevent a) or b).

e) any indirect harm as a consequence of incorrect diagnostic test results when used within manufacturer's instructions for use.

• Fetal distress, fetal death, congenital abnormality or birth defect including physical or mental impairment. Note: Planned hospitalization for a preexisting condition, or a procedure required by the CIP, without serious deterioration in health, is not considered a serious adverse event.

 
Refer to Section 11 for additional SAEs.

-----------------------------	---

Serious Health Threat	
Signal from any adverse event or device deficiency that indicates an imminent risk of death or a serious deterioration in the health in subjects, users, or other persons, and that requires prompt remedial action for other subjects, users, or other persons.
 
Note: This would include events that are of significant and unexpected nature such that they become alarming as a potential serious health hazard or possibility of multiple deaths occurring at short intervals.

Study Start	The start of the study is considered to coincide with the enrollment of the first patient.
Study Completion	The completion of the study is considered to coincide with the study-level last subject last visit or the decision to terminate the trial, whichever is later.

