### **11.3 Return product analysis (as applicable)**

Alcon products associated with device deficiencies and/or product related AEs should be returned and must include the Complaint # which will be provided by study sponsor after the case is entered in the study sponsor's Global Product Complaint Management System. These products should be returned to the sponsor at the end of the study, unless instructed otherwise by the sponsor.

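### Section 11.2 gives every device deficiency the same 10-calendar-day limit for reporting to the sponsor, including one that signals a Serious Health Threat or could have led to a SADE before any SAE has occurred

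*Protocol*

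**What the plan says.** Protocol Section 11.2 introduces site-to-sponsor reporting with one instruction: "The site must submit all available information on ADEs, SAEs, and device deficiencies to the study sponsor immediately as follows". Two limits follow, both counted from awareness by the investigator or site. SAEs have 24 hours. For everything else in scope, "ADEs that do not meet seriousness criteria and Device deficiencies must be reported within 10 calendar days". That bullet does not grade deficiencies by what they might lead to.

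Three other places bear on the same events:

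- The Glossary (Section 1) defines a Serious Health Threat as a "Signal from any adverse event or device deficiency that indicates an imminent risk of death or a serious deterioration in the health" of subjects, users or others, and one "that requires prompt remedial action for other subjects, users, or other persons". It names no actor and no time limit, and the term does not reappear in the Section 11 text provided.
- The Device Deficiencies text in Section 11 says: "A device deficiency may or may not be associated with patient harm (i.e., ADE or SADE"). Its examples include possible contamination, labelling errors and seals that have been tampered with.
- Later in Section 11.2 the investigator must also report AEs and "device deficiencies that could have led to a SADE according to the requirements of regulatory authorities or IRB/IEC". No number of days is given there, and the sponsor is not named as recipient.

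**The concern.** The protocol recognises two kinds of deficiency that matter before anyone is seriously hurt: one that signals a Serious Health Threat, and one that could have led to a SADE. Neither is an SAE merely by existing, so neither reaches the 24-hour route on its own. Both fall by default under the slower limit. The lead-in points towards speed, but a site that needs a compliance deadline will work to the number in the bullet.

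What is at stake is the time until the sponsor can act. The sponsor supplies both lenses to about 8 sites (Sections 8 and 9.1). Lenses go home with subjects at Visits 1 and 2, and no scheduled visit falls between dispensing and follow-up (Section 10). Section 7.5 provides for no data monitoring committee. A signal held at one site is therefore unlikely to reach the other sites except through the sponsor.

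**Working it through.** No statistical formula applies. The check sets the reporting limit against the visit calendar and then reads the passages together.

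**Inputs.** Reporting limits: 10 calendar days and 24 hours (Section 11.2). Visit spacing: 8 (-0/+3) days for each lens (Section 10), so 8 to 11 days. Maximum participation: 22 days (Section 7.1). Total exposure: 16 days (Tables 9-1 and 9-2).

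**The plan's own calendar.** Maximum participation = 2 × (8 + 3) = 22 days. Nominal exposure = 2 × 8 = 16 days. Both match the protocol.

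**Limit against wear period.**

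| Wear period (days) | 10 minus wear period (days) |
|---|---|
| 8 (nominal and minimum) | +2 |
| 9 | +1 |
| 10 | 0 |
| 11 (maximum) | -1 |

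**Timing when the site learns of the deficiency at Visit 2** (Visit 1 = day 0):

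- Visit 2 on day 8: the report is due by day 8 + 10 = 18. Visit 3 may fall on days 8 + 8 = 16 to 8 + 11 = 19.
- Visit 2 on day 11: the report is due by day 21. Visit 3 may fall on days 19 to 22.

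In either case a subject dispensed lenses on the day the site became aware could complete a nominal 8-day period before a compliant report was due.

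**Which events are exposed.**

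1. A deficiency that has already produced an SAE is not in the gap, because the SAE goes to the sponsor within 24 hours.
2. A deficiency with no adverse event, or only a nonserious one, is on the 10-day limit whatever its potential.
3. The duty to report deficiencies that could have led to a SADE runs to the requirements of authorities or the IRB/IEC. It may be faster in practice, but it sets no sponsor limit.

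**After the fix.** On the existing 24-hour route the longest permitted lag for these events falls from 10 days to 1, or from 10/8 to 1/8 of a nominal wear period.

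**The case against.** The case on the other side has several good parts.

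- *The lead-in already asks for immediate reporting.* This stands as mitigation: 10 days is an outer limit, not an expected delay. It does not close the gap, because a day-10 report still complies with the bullet.
- *The Glossary defines a signal and imposes no duty.* Correct. A reader might infer that Section 11.2 breaches a Glossary requirement for remedial action. It does not: the definition assigns no action, actor or deadline. The point is that a class the protocol names has no matching sponsor limit.
- *The 24-hour route is wider than harm already done.* A reader might infer that it covers only completed injury. The SAE definition includes events that could potentially threaten sight, and interventions to prevent serious outcomes, so early ocular events of that kind are already covered. The remaining gap is narrow, and none of the listed deficiency examples is by itself a Serious Health Threat.
- *Early product return is already possible.* Section 11.3 says: "These products should be returned to the sponsor at the end of the study, unless instructed otherwise by the sponsor". Section 9.5 has a similar exception. This stands, and Section 11.3 needs no change.
- *Comparator lenses have another route.* Section 10.2.6 sends comparator deficiencies to the manufacturer's process. Section 11.2 nonetheless requires deficiencies of both lenses on the eCRF, so the 10-day bullet still applies to both.

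A reader might also infer that a dangerous lot would reach some 61 further subjects (128 / 21 × 10, taking 3 weeks as 21 days and accrual as even). The documents do not support that figure. It counts consented subjects; on the 116 treated it is 116 / 21 × 10 = about 55. Either number is a ceiling that needs 10 days of recruitment still to run, so the fault would have to be found by about day 11 of 21. Nothing says subjects share a lot: there are two products, and powers run from -1.00 to -6.00 D in 0.25 D steps.

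**Conclusion.** The point holds in a limited form. A deficiency found before any SAE, but signalling a Serious Health Threat or able to have led to a SADE, may compliantly reach the sponsor up to 10 calendar days after the site knows of it. That exceeds the nominal 8-day wear period by 2 days and falls 1 day short of the 11-day maximum. It is a permitted worst case, not an expected delay, and any time before the site becomes aware comes on top of it.

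The severity is minor: low probability, potentially serious consequence, very cheap to correct. Device deficiencies are only tabulated and listed (SAP Section 5.3.3), so no endpoint, power figure or analysis is affected.

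The conclusion rests on the text provided. Figures 11-1 and 11-2 are not shown and the MOP was not available, so a faster route in either cannot be ruled out. If one exists, Section 11.2 need only refer to it.

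**What to change.** Split the second reporting bullet in Section 11.2:

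- Any AE or device deficiency that signals a Serious Health Threat, and any device deficiency that could have led to a SADE, goes to the sponsor on the 24-hour route that Section 11.2 already has for SAEs. Naming AEs as well as deficiencies keeps the bullet in line with the Glossary term, which covers both.
- All other device deficiencies and nonserious ADEs keep 10 calendar days.

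Add a flag for the first group to the Device Deficiency eCRF. The split also reconciles the lead-in's *immediately* with the limits listed beneath it. The cost is one protocol bullet, one eCRF field and a few faster reports from sites.
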